### **Subgroup analyses**

Given the potential for treatment to have different effects on individuals or specific groups, tests for heterogenous treatment effects will be performed to analyse whether individuals respond differently to treatment based on three observable characteristics: sex, ethnicity, and referral source. In this case, we will estimate the regressions specified above for subsamples based on these characteristics (male, female, white, non-white, police, youth services). Although the individual randomisation process was not stratified based on these

---

 The subgroup analysis will not be done in interactions of subgroups due to sample size limitations.

groups, if the sample size is sufficiently large to do a powered analysis, reporting results for groups defined post-randomisation could provide supplementary insights alongside the primary findings (Duflo et al. 2007). Therefore, this part of the analysis will also be exploratory, and we acknowledge potential limitations in terms of statistical power, since the sample size for each subgroup will be small.

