This is a newly developed intervention introduced in Spring 2022, as part of the pilot study undertaken by the current research team. As part of this efficacy study, the intervention will run from April 2023 until April 2025.

CYP will be referred to Remedi via the police and youth justice services on a consent-based voluntary basis. Remedi reports that these CYP frequently have low levels of awareness / understanding / empathic awareness regarding the impact of their behaviours, have problematic issues within their familial setting and face varying levels of challenges regarding

² Remedi ask for further information around these offences to understand the circumstances and whether the CYP was displaying violent behaviour when in possession.

their mental and/or emotional health. In the experience of Remedi, if unsupported these behaviours often result in greater degrees of violence/criminality³.

The RM intervention consists of three components, to provide intensive one to one support for CYP. All CYP in the intervention group will receive the mentoring component but what, if any, other component they receive will be determined by an initial needs assessment of the CYP. This takes place during an initial contact meeting between the mentor and CYP and considers the following areas of a CYP's life: relationships with parents/carers, educational attendance, mental health, self-esteem and peer pressure, emotional regulation, dealing with people in authority. The result of this assessment informs the creation of a support plan for the CYP⁴.

The three components of RM are:

i. Mentoring: This element will last for around 12 weeks, based on 3-4 1-to-1 sessions per week. The content of these sessions is determined through the creation of an 'Action Plan' agreed with the CYP with Specific, Measurable, Achievable, Relevant and Time-bound (SMART) goals and expectations established.

ii. Restorative Justice (RJ): Provision of a full RJ intervention (whether direct or indirect) with harmed individuals identified and willing to take part RJ will be offered and mentioned during the mentoring work to give many opportunities to take part – using Remedi's empathic thinking work during the mentoring. An RJ intervention will not be able take place without an identified or willing victim

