The overarching objective is to explore whether the RM intervention has greater impact than the RC intervention in terms of CYP's contact with the police and emotional and behavioural difficulties. The study has the following research questions:

1. What is the impact of the RM intervention on the contact with the police of CYP who experience it?
 - a. Is this greater than the impact of the RC intervention?
2. What is the impact of the RM intervention on the emotional and behavioural difficulties of CYP who experience it?
 - a. Is this greater than the impact of the RC intervention?
3. Does any impact vary across subgroups, including CYP demographic characteristics (age, sex and ethnicity) and the exact variant of the RM intervention received (which combination of the three elements received; mentoring, restorative-based family support, restorative justice).⁶

To achieve the overarching objective of the impact evaluation, it is necessary that:

- Regular fidelity checks are carried to ensure that the approved protocol is closely followed;
- That the blinding arrangements are in place;
- Data collection is regularly observed for timeliness and consistency;
- The necessary number of CYP recruitment is reached;
- The data are analysed according to the Statistical Analysis Plan.

YEF will not have any role in the collection or interpretation of the data, or in the decision to submit results.

We will be required to provide monitoring information to the funder quarterly on the progress of the study.

⁶ This will be examined via exploratory analyses.

Any changes to the protocol will be logged in a change log following discussion with the provider and funder.

Design

The trial will be a two-armed (RM and RC) individually randomised controlled trial. Upon referral to Remedi, CYP who have committed a violent offence or have displayed violent behaviours will be randomly assigned to RM (the treatment group) or RC (the control group) on a 1:1 basis.

Table 1: Randomized Control Trial protocol

Step 1:	CYP is referred to Remedi
Step 2:	Remedi assesses eligibility. Ineligible cases are excluded.
Step 3:	Informed consent/assent is provided by eligible CYP.
Step 4:	Data on CYP are collected (SDQ, SRDS questionnaires).
Step 5:	Randomisation done by the University of Birmingham: CYP is assigned to RM or RC.
Step 6:	CYP receives RM or RC.
Step 7:	Right after the interventions are completed, data on CYP are collected (SDQ, SRDS questionnaires) for short-term outcomes.

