The planned number of the trial participants is 352 CYP in its two years of implementation, 176 in the RM group and 176 in the RC group. The sample size is such that the trial is sufficiently powered to detect a Cohen's d of at least 0.3. At the same time, the sample size is in line with the recruitment capacity, funder guidelines and the previous literature, see e.g. O'Connor and Waddell (2015) for a review. The mean effect sizes found in that paper for youth violence interventions range between 0.19-0.4. The calculations are done in Matlab based on Rosner (2011).

Table 3: Sample size calculations

⁷ Community resolution, Youth caution, Youth conditional caution, plus CYP who have been in contact with the police for a violent offence, but no further action has been taken.

		PARAMETER
Minimum Detectable Effect Size (MDES)		0.3
Alpha		0.05
Power		0.8
One-sided or two-sided?		Two-sided
Number of participants	Intervention	176
	Control	176
	Total	352

The above calculations report the sample size for the whole study over a two-year period.

Outcome measures

Primary outcome

The primary outcome of interest is the number of contacts of the CYP with the police, as perpetrators, victims or missing person episodes⁸. This will be measured using police administrative data from Greater Manchester Police (COGNOS system). Data will be taken for a period 1 year prior to the recruitment date and 3 months following the end of the interventions for each CYP. Police contact data is a discrete variable starting at 0.

This is a broad definition and was chosen because the CYP being referred to the RM or RC interventions were expected to have only had limited contact with the police. As a result, relying only on subsequent arrests and proven offending risked minimising their further contact with the police.

Secondary outcomes

The secondary outcomes will be the CYP's emotional and behavioural difficulties (as measured by the Strengths and Difficulties Questionnaire, SDQ) and self-reported delinquency (as measured by the Self-Report Delinquency Scale, SRDS).⁹ CYP will complete these at the point of consent, at the end of the interventions and 6 months

⁸ In cases where a CYP was arrested and rearrested for the same offence, we would create a rule that as this relates to the same offence, this would count as one arrest.

⁹ Full questionnaires for both the SDQ and SRDS are provided at Appendix 2.

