Furthermore, as it is expected that compliance will not be perfect, the analysis will involve estimating a local average treatment effect (LATE), which will provide an estimate of the treatment effect for individuals who engage with the intervention (Imbens & Wooldridge, 2007; Angrist, 2014). In this case, treatment assignment will be used as an instrument for whether individuals get treated or not.

Given the potential for treatment to have different effects on individuals or specific groups, tests for heterogeneous treatment effects will be performed to analyse whether individuals respond differently to treatment based on observable characteristics such as sex and ethnicity. Although the individual randomisation process was not stratified based on these groups, if the sample size is sufficiently large to do a sufficiently powered analysis, reporting results for groups defined post-randomisation could provide supplementary insights alongside the primary findings (Duflo et al. 2007). This is also the case for the groups of CYP who have received the different elements of the RM intervention (mentoring, restorative-based family work and RJ). We consider the RM intervention to be one intervention provided to CYP, but if the sample size is sufficiently large to achieve statistical significance, reporting results for groups who have received different components will be considered.

Longitudinal follow-ups

Police administrative data for the primary outcome will be gathered one month prior to the end of the trial, allowing a three-month follow-up for all CYP.

Follow-up data for the secondary outcome measures will be collected 6 months following the end of the interventions (for those CYP who begin the interventions during the first 18 months of the study). These data will allow the evaluation of the longer-term impact of the intervention. We will perform a follow-up analysis that mirrors the approach outlined in the previous section, incorporating the data collected during the 6-month post-intervention period.

Table 4: Impact Evaluation Methods overview

Research methods	Data collection methods	Participants/ data sources (type, number)	Data analysis methods	Research questions addressed

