### Sample size calculations overview

	Protocol	Randomisation
Minimum Detectable Effect Size (MDES)	0.3	0.3
Alpha	0.05	0.05
Power	0.8	0.8

		Protocol	Randomisation
One-sided or two-sided?		Two-sided	Two-sided
Number of participants	intervention	176	176
	control	176	176
	total	352	352

The planned number of the trial participants is 352 CYP in its one year of implementation, 176 in the RM group and 176 in the RC group. The sample size is such that the trial is sufficiently powered to detect a Cohen’s d of at least 0.3 with probability 80%, which is in line with the funder guidelines and the previous literature.

The “simple” randomisation method will be used, which is a robust method against selection and accidental biases. We will use the statistical software package Matlab to implement the randomisation. Automated randomisation will ensure that the process is transparent and reproducible.

The above rest on the assumption that the alpha is equal to 0.05 and that the power is equal to 0.8. The minimum detectable effect size is equal to 0.3 as measured by Cohen’s d.

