### **Secondary outcome analysis**

In this part of the analysis, the aim is to answer the research question: did the Restorative Mentoring intervention (treatment) reduce difficulties and self-reported behaviour measures according to the SDQ and SRDS questionnaires, when compared to the Restorative Choices intervention (control). Furthermore, do these reductions differ by sex, ethnicity, and referral source.

The secondary outcomes for this analysis will include the CYP's emotional and behavioural difficulties and self-reported delinquency.

Emotional and behavioural difficulties are measured by the following three variables:

- 1) Internalizing score – measured on a scale from 0-20
- 2) Externalizing score – measured on a scale from 0-20
- 3) Total difficulties score – measured on a scale from 0-40

Self-reported delinquency is measured by:

4) Variety of delinquency - measured as the sum of the overall categories of delinquency  
Range: 0-19.

5) Volume of delinquency - measured as the sum of magnitudes of delinquency, over all  
categories Range: 0-198.

These variables will be compared across the treatment and control groups to test the null hypothesis of equal means against the two-sided alternative.

The regression analysis takes the form

$$Y_i = \alpha + \beta T_i + Z_i' \gamma + u_i \quad (2)$$

where  $Y_i$  is the secondary outcome for individual  $i$  (one of the aforementioned SDQ and SRDS variables).  $T_i$  is an indicator variable equal to 1 if  $i$  was assigned to treatment and 0 if  $i$  was assigned to the control group.  $Z_i$  is a vector of individual characteristics that are not affected by the intervention (sex, age, ethnicity, district, prior contact with the police, and referral source).  $u_i$  represents the random errors, which are not observed. Given that  $Y_i$  is a continuous variable we will employ a linear regression. The key assumptions that we will use is that the observations are independent to each other, there is mean independence  $E(u_i|T_i, Z_i) = 0$ , and that not all CYP have identical  $T_i$  and  $Z_i$  (no perfect multicollinearity). These assumptions are weak and easily satisfied.

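### The SAP asks whether the effect of RM differs between subgroups but plans only separate subsample regressions, which do not test a difference; component reporting and the subgroup lists also need repair

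*SAP*

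**What the plan says.** Research question 3 (Protocol, Research questions or study objectives) asks whether impact varies by age, sex and ethnicity, and by "the exact variant of the RM intervention received". A footnote there marks this as exploratory.

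The SAP (Subgroup analyses) names sex, ethnicity and referral source. It describes its purpose as testing for heterogeneous effects, and its method is: "we will estimate the regressions specified above for subsamples based on these characteristics". The subsamples are male, female, white, non-white, police referrals and youth service referrals. The SAP's Secondary outcome analysis asks the same kind of question of the SDQ and SRDS scores. The regressions referred to contain the treatment indicator, with or without baseline covariates, and no product of treatment and subgroup. Footnote 3 only rules out crossing one subgroup variable with another. The section calls the work exploratory, expects small subgroups, and links reporting to a sample large enough for a powered analysis.

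On components, the Protocol (Impact evaluation, Analysis) regards RM as one intervention but adds: "if the sample size is sufficiently large to achieve statistical significance, reporting results for groups who have received different components will be considered". Every RM participant gets mentoring; beyond that, "what, if any, other component they receive will be determined by an initial needs assessment of the CYP" (Protocol, Intervention). The same section says that family work may also be prompted by the referring professional, the CYP or the mentor, and that restorative justice needs an identified and willing victim. The SAP has no analysis of components or of age.

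**The concern.** Whether an effect differs between boys and girls is a question about the contrast between two effects. Two p-values, one from each subsample, do not estimate that contrast or attach an uncertainty to it. When each subsample has middling power, one will often be significant and the other not even though the true effects are equal. Research question 3 is a named question, and an apparent finding that RM suits one sex or ethnic group could influence who is offered it.

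Components raise a different problem. Those beyond mentoring are not randomised and exist only in RM, so RC contains no identifiable comparable group. A comparison of, say, RM participants who had family work with all of RC mixes the effect with the reasons for receiving it. Making such results depend on a sample large enough to reach significance also invites selection on the result.

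**Working it through.** **Inputs.** Sample size: "The planned number of the trial participants is 352 CYP in its two years of implementation, 176 in the RM group" (Protocol, Sample size calculations), allocated 1:1. Error rates: "The above rest on the assumption that the alpha is equal to 0.05 and that the power is equal to 0.8"; effect size: "The minimum detectable effect size is equal to 0.3 as measured by" Cohen's d (both SAP, Sample size calculations overview). The sample size table is two-sided, and the secondary outcomes are compared "to test the null hypothesis of equal means against the two-sided alternative". Expected questionnaires: 148 at end point and 35-70 at six months (SAP, Design overview). The share s in the larger level of each characteristic is in neither document; I assume 50% to 90%.

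**The plan's own figure.** n per arm = 2(1.96 + 0.842)²/0.3² = 174.4, so 175 by the normal approximation. The t-based value is 175.4, so 176 per arm and 352 in total, which reproduces the plan. Power with 176 per arm is Φ(0.3/√(2/176) − 1.96) = 80.4%.

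**Subsamples, effect d = 0.3 in everyone.** SE in a level of size Ns is 2/√(Ns), and power is Φ(0.3/SE − 1.96) plus a negligible lower tail. The two levels are disjoint, so the chance that exactly one is significant is p₁(1 − p₂) + p₂(1 − p₁). At 50/50: SE = 2/√176 = 0.151, power = Φ(0.03) = 51.2%, discordance = 2 × 0.512 × 0.488 = 50%. At 80/20: powers 71.1% and 24.2%, discordance = 0.711 × 0.758 + 0.242 × 0.289 = 61%.

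| Split | Power, larger / smaller level | Exactly one significant | Interaction power for a 0.3 difference | Difference detectable at 80% power |
|---|---|---|---|---|
| 50/50 | 51% / 51% | 50% | 29% | 0.60 |
| 70/30 | 65% / 34% | 55% | 25% | 0.65 |
| 80/20 | 71% / 24% | 61% | 20% | 0.75 |
| 90/10 | 76% / 14% | 69% | 14% | 1.00 |

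Simulation (6,000 trials per scenario, the three characteristics taken as unrelated) agrees. At least one of the three is discordant in 75% of trials (all 50/50) to 82% (80/20, 70/30, 60/40).

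**Other scenarios.** With no effect in anyone: 2 × 0.05 × 0.95 = 9.5% per characteristic, about 10% in simulation, and 22% for at least one of three. For the questionnaires at d = 0.3: 38-43% with 148 returned and 17-26% with 35-70 returned.

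**Interaction test.** SE = √(4/(Ns) + 4/(N(1 − s))). At 50/50 this is √(4/176 + 4/176) = 0.213, so power for a 0.3 difference is Φ(0.3/0.213 − 1.96) = 29%. The false-positive rate is about 5% per characteristic whatever the overall effect. Over three it is 1 − 0.95³ = 14%, or 15% in simulation. Detecting a 0.3 difference with 80% power would need about 1,395 participants at 50/50 and 2,180 at 80/20. With 148 questionnaires, interaction power is 9-15%.

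**The SAP's reporting condition.** The whole trial has only 80.4% power for d = 0.3, so no subgroup can reach 80% for that effect. A half-sample subgroup can detect 0.42, and a 20% subgroup 0.67.

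**Components.** Suppose 10%, 20%, 30% or 50% of RM receive a component (assumed; 18, 35, 53 or 88 CYP) and are compared with all 176 in RC. Power for d = 0.3 is 22%, 37%, 48% and 63%. If only significant results were then shown, the reported effect would average 2.1, 1.6, 1.4 and 1.3 times the true one. That is before any confounding by need.

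**The case against.** The strongest defence is that both documents call these analyses exploratory and the SAP admits low power, so nothing confirmatory rests on them. That stands, and it limits the point to how research question 3 is interpreted. It does not turn two within-group results into a test of a difference, and low power is what makes discordance common.

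Three stronger readings are tempting, and the documents do not support them.

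- A reader might infer that the plan will declare RM effective in one group and not another. No such rule is written. The 50-69% is the frequency of a pattern, not of a declared difference, so it is not on the same footing as the interaction test's 5%. Subsample estimates could also be contrasted directly; the gap is that the SAP does not say so. Its condition about a powered analysis, read literally, would discourage subgroup reporting altogether.
- A reader might infer that component results are published only when p < 0.05. The Protocol's condition is on sample size, and it says only that reporting will be considered. The wording invites selection but does not prescribe it, and the SAP contains no component analysis at all.
- A reader might infer that the answers will be mostly noise. The high discordance belongs to one scenario, a uniform d = 0.3 on the primary outcome. It is about 10% per characteristic with no effect, and below one half for the questionnaires.

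It is also fair to say that the better method leaves the question largely unanswered at this sample size.

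**Conclusion.** The point holds for the method. The SAP poses a question about differences between effects and specifies analyses that do not estimate or test a difference. Under the design effect applied uniformly to the primary outcome, discordant significance occurs in about 50% (50/50) to 69% (90/10) of trials per characteristic. This rests on assumed subgroup shares, unadjusted comparisons and a normal approximation. The primary conclusion is unaffected.

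On components, two narrower statements hold: the significance wording invites selection, and components beyond mentoring have no randomised comparator in RC.

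The lists also conflict. Research question 3 has age, sex, ethnicity and component mix; the SAP has sex, ethnicity and referral source, leaving age and components without an analysis.

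**What to change.** - **SAP, Subgroup analyses.** For each listed characteristic, fit one full-sample model with a treatment-by-subgroup term. State its scale: a ratio of rate ratios under the log link, a difference in means under the linear model. Report every interaction estimate with its confidence interval regardless of significance, and show subgroup effects as description only.
- **Same section.** State the limits: about 29% power at 50/50 and 20% at 80/20 for a 0.3 difference, and about a 15% chance of at least one false positive over three characteristics. Replace the condition about a powered analysis, which no subgroup can meet for d = 0.3.
- **Protocol, Analysis.** Remove the achievement of statistical significance as a condition for considering component results. Present any such results as a description within RM, with no effect estimate against RC.
- **Both documents.** Agree one list of characteristics. Either give age an analysis in the SAP or take it out of research question 3, state where referral source belongs, and say how component mix will be described.

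The cost is wording plus one model term per characteristic, using the same data. The change corrects the inference; it does not add power.

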### **Interim analyses and stopping rules**

No such analysis is planned as it will be underpowered. The pilot study gave sufficient evidence for the safety of the intervention.

### **Longitudinal follow-up analyses**

One follow up point for measurement is specified – 6 months after the end of the intervention for the secondary outcomes. This will enable the estimation of potential longer lasting effects of the intervention by performing the same statistical analysis described above with data covering a longer period of time.

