In the pilot study 73% of CYP consented into the interventions completed the initial questionnaires, and 42% completed the end point questionnaires. We would expect these rates to be similar for this efficacy study and so could expect to receive 257 initial questionnaires and 148 end point questionnaires. Six-month follow up questionnaires were not completed as planned during the pilot study and so we cannot use these completion rates to estimate the expected number of completed questionnaires during the efficacy study. However, we would expect completion rates to be lower than those at the end of the interventions, due to the break in contact with the CYP. As such as estimate between 10-20% of CYP will complete these questionnaires, which would equate to between 35-70 questionnaires.

While these are the outcomes of interest to the study, Remedi believes that the RM intervention has a series of short, medium, and long-term outcomes which are outlined above in the theory of change for the RM intervention. Most of these cannot be quantified within the evaluation period, though the process evaluation will capture some of the subjective measures.

Compliance

Compliance will be ensured by implementing a regular fidelity check agreement. The list of indicators to monitor include:

1. *To ensure the program is implemented by Remedi as designed and improve quality and programme fidelity, it is necessary to guarantee:*
 - Children and young people (CYP) referred to Remedi are eligible.
 - Inform/consent is signed before randomisation.
 - Baseline data is appropriately collected before randomisation.
 - CYP receive the correct result RM or RC.
 - Final data is appropriately collected at the end of the intervention.

2. *To avoid threats to internal validity it is necessary to consider:*
 - Attrition – monitor CYP who disengage and do not participate in the final data collection.
 - Compliance – monitor the engagement of the CYP with the interventions, assessed by whether they complete the programme or not, using data

recorded on the Remedi CMS (e.g., if they change their minds and disengage, do not engage in the sessions, etc.)

- Spill overs – unlikely - treatment and control groups are not likely to communicate.
- Evaluation-driven effects (CYP changing their behaviour in response to the evaluation instead of the intervention) – can look at outcomes from the administrative data.

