	
measure(s) (instrument, scale, source)
	
The first three scores are measured with the Strengths and Difficulties Questionnaire (SDQ). The remaining two scores (4 & 5) are measured with the Self-Reported Delinquency Scale (SRDS).
 
The SDQ and SRDS are completed by CYP at the point of consent, end of the intervention and 6 months after the end of the intervention as a follow-up (for CYP who start the interventions in the first 18 months of the trial).
 
For the SDQ CYP are asked to recall over the past 6 months, a period defined in the measure. For the SRDS, CYP are asked to recall over the past 3 months, this was a period defined for this study, in consultation with Remedi.
 
Scales are 0-20 for the internalizing and externalizing scores and 0-40 for the total difficulties score. Variety of delinquency ranges from 0-19 and volume of delinquency ranges from 0-198 (this excludes the scoring for Question 16, which is different from the other questions).
 
In the pilot study 73% of CYP consented into the interventions completed the initial questionnaires, and between one third and one half completed the end point questionnaires. We would expect these rates to be similar for this efficacy study and so could expect to receive around 257 initial questionnaires and 148 end point questionnaires. Six-month follow up questionnaires were not completed as planned during the pilot study and so we cannot use these completion rates to estimate the expected number of completed questionnaires during the efficacy study. However, we would expect completion rates to be lower than those at the end of the interventions, due to the break in contact with the CYP. As such we estimate between 10-20% of CYP will complete these questionnaires, which would equate to between 35-70 questionnaires. The expected attrition rate will affect the power of the analysis for these secondary outcomes.

Baseline for primary outcome
	
variable
	
The primary outcome of interest is the number of contacts of the CYP with the police, as perpetrators, victims or missing episodes.

	
measure (instrument, scale, source)
	
Police contact data will be taken from Greater Manchester Police administrative records for events 1 year prior to the intervention. Police contact data is a discrete count variable starting at 0.

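### The six-month SDQ/SRDS contrast is planned as a cross-sectional rerun on 35-70 forms; a joint model using the baseline and closing scores would be a cheap improvement

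*SAP*

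**What the plan says.** The SAP (Longitudinal follow-up analyses) obtains the six-month effect on the secondary outcomes by "performing the same statistical analysis described above with data covering a longer period of time". The protocol (Longitudinal follow-ups) agrees: "We will perform a follow-up analysis that mirrors the approach outlined in the previous section".

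The analysis referred to is in the SAP, Secondary outcome analysis. It is a comparison of arm means plus equation (2), Y_i = α + βT_i + Z_i′γ + u_i, chosen because the score "is a continuous variable we will employ a linear regression". The covariates Z are "sex, age, ethnicity, district, prior contact with the police, and referral source". There is no time index and no within-person covariance, and no baseline or closing SDQ/SRDS score enters.

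On numbers, the SAP (Design overview) says the trial "could expect to receive around 257 initial questionnaires and 148 end point questionnaires". For the six-month forms, "we estimate between 10-20% of CYP will complete these questionnaires", given as 35-70 forms. The same instruments and scales are used at all three visits.

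The SAP calls the secondary analysis exploratory, says it describes those who finish, and warns of limited power. Its Missing data section offers imputation or sensitivity analyses only for missing control variables. No remedy is given for unreturned SDQ/SRDS forms.

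**The concern.** A CYP who returned a closing form but no six-month form adds nothing to the six-month contrast, although the closing score is the most recent measurement on the same scale. It cannot simply be added to equation (2), because it is measured after randomisation and may itself be affected by treatment.

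Two things are at stake. One is precision, in an analysis that is already very small. The other is bias: if CYP who are doing badly at closing are less likely to return the later form, and this tendency differs between RM and RC, the two groups of responders are no longer comparable. The closing scores would show this, but the planned model cannot use them. Both documents present the six-month data as evidence on longer-term effects.

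**Working it through.** **1. The plan's own counts.** The protocol (Secondary outcomes) gives 73% for initial forms and "42% completed the end point questionnaires".
- Baseline: 352 × 0.73 = 256.96, stated as 257.
- Closing: 352 × 0.42 = 147.84, stated as 148.
- Six months: 352 × 0.10 = 35.2 and 352 × 0.20 = 70.4, stated as 35-70.

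All reproduce. The 10-20% is taken of all 352, but the protocol Timeline approaches only CYP consented by 31 July 2024, while recruitment runs to 30 November 2024. If recruitment were even from May 2023 (assumption: 15 of 19 months), 352 × 15/19 = 277.9, and 10-20% of that is about 28-56 forms.

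**2. Six-month forms alone.** Two-sided alpha 0.05, power 0.8, 1:1 allocation, SD = 1. MDES = (1.96 + 0.84) × √(4/N).
- N = 35: MDES 0.95; power at d = 0.3 is 14%.
- N = 70: MDES 0.67; power at d = 0.3 is 24%.

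**3. Adding closing scores only.** Assume everyone with a six-month form also has a closing form, and that return is random. Maximum likelihood then multiplies the variance by f = 1 − ρ²(1 − n₆/148), where ρ is the closing to six-month correlation. The documents do not give ρ, so a range is shown.

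| ρ (assumed) | 35 forms: f, SE cut, MDES, power | 70 forms: f, SE cut, MDES, power |
|---|---|---|
| 0.3 | 0.931, 3.5%, 0.91, 15% | 0.953, 2.4%, 0.65, 25% |
| 0.5 | 0.809, 10.0%, 0.85, 17% | 0.868, 6.8%, 0.62, 27% |
| 0.6 | 0.725, 14.8%, 0.81, 18% | 0.810, 10.0%, 0.60, 29% |
| 0.7 | 0.626, 20.9%, 0.75, 20% | 0.742, 13.9%, 0.58, 31% |
| 0.8 | 0.511, 28.5%, 0.68, 24% | 0.663, 18.6%, 0.55, 34% |

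Example: ρ = 0.6 with 35 forms gives 1 − 0.36 × (1 − 35/148) = 1 − 0.36 × 0.764 = 0.725.

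**4. All three visits.** Simulation of 352 CYP with normal scores. Assumptions: true six-month effect -0.30 SD; 73% baseline and 42% closing forms at random; six-month forms only from those with a closing form; correlations 0.6 (baseline-closing), 0.5 (baseline-six-month) and 0.6 (closing-six-month). With random return, the joint model's variance is about 26-28% below the raw six-month difference and 15-16% below six-month ANCOVA on baseline. At correlations 0.5/0.4/0.5 with 35 forms, the gain over the raw difference is 18%.

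**5. Selective return.** Same settings, with the log-odds of returning the six-month form falling 0.7 per SD of worse closing score. Ranges cover 35 and 70 forms.

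| Who is selected | Six-month forms only | Joint model |
|---|---|---|
| RM only | -0.48 to -0.56 | -0.29 to -0.31 |
| Both arms alike | -0.28 to -0.29 | not needed: little bias |

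With a two-visit model and the same RM-only slope, six-month forms alone average -0.45 to -0.53 at ρ = 0.5 and -0.51 to -0.61 at ρ = 0.7.

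**6. Where the joint model fails.** If the same RM-only selection acts on return of the closing form itself, the joint model averages -0.43 to -0.44, no better than six-month ANCOVA on baseline. If return depends on the unseen six-month score, the joint model averages -0.51 to -0.59.

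**The case against.** The strongest case against is that little follows from this.

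- **Disclosure.** The SAP already labels the analysis exploratory, restricted to those who finish, and low-powered. That stands, and it limits how much the point matters. But the SAP mentions attrition only as a matter of power, and holds data that could partly address selective return.
- **Bias.** A reader might infer that the planned estimate is unbiased only if return of the form is unrelated to closing state. That is wrong: equal dependence in both arms leaves the contrast nearly intact. The large bias needs arm-differential selection, and the documents give no return rates by arm. Such selection is conceivable, since RM involves 12 weeks of frequent contact and RC four sessions, but the RM-only scenario is chosen for illustration.
- **The larger loss comes earlier.** The fall from 352 CYP to 148 closing forms is the bigger selection step, and those missing closing scores are unseen. A reader might infer that a joint model removes attrition bias; step 6 shows that it does not.
- **The comparator.** The simulated comparators omit Z. If those covariates are prognostic, the gain over the actual plan is smaller. A joint model without Z could also lose protection that equation (2) has, so Z must stay in.
- **Fit.** RM closes at about 12 weeks and RC within one to four, so with six-month SDQ recall an RC closing form largely overlaps the baseline window and correlations may differ by arm. SRDS volume (0-198) is count-like, while only normal data were simulated.
- **Wording.** Reading the plan as a separate regression is an inference from loose text. It is the natural one, because no repeated-measures model appears anywhere. Nor are the closing scores discarded: they have their own analysis.

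**Conclusion.** The point holds as a cheap improvement. As written, the six-month contrast uses only the expected 35-70 six-month forms and draws nothing from about 148 closing and 257 baseline scores on the same scales.

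The likely variance saving is about 26-28% against an unadjusted comparison and 15-16% against baseline ANCOVA. Both figures rest on assumed correlations of 0.5-0.6; the saving is less at lower correlations or with prognostic Z. Material bias in the planned estimate requires that return depends on closing score differently by arm.

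A reader might also infer that the joint model rescues the six-month analysis. It does not: on closing scores alone, power at d = 0.3 rises from 14-24% to at most about 34%, even at a correlation of 0.8.

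**What to change.** For each SDQ and SRDS score, make the main six-month analysis one repeated-measures model:

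- outcomes: the baseline, closing and six-month values, including every CYP with at least one form;
- means: a common baseline mean, arm-by-visit means after baseline, and the covariates Z of equation (2);
- covariance: unstructured, fitted by REML, with a simpler structure named in advance in case it does not converge;
- estimate: the RM-RC contrast at six months.

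Keep the six-month-only regression as a sensitivity analysis. State in the SAP that closing forms fall at different times in RM and RC; that the model assumes missing at random given observed scores and Z; that it does not correct selection on unseen closing or six-month scores; and that the result stays exploratory and low-powered.

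The cost is SAP wording, a matching line in the protocol, and one standard mixed model per score. No new data are needed.
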